To compare the efficacy of branebrutinib with PBO at Week 24 in the treatment of subjects with pSS	 Proportion of subjects with at least 3 of the following at Week 24: Decrease of ≥ 1 point or 15% from baseline in the ESSPRI Total Score Decrease of ≥ 3 points from baseline in ESSDAI score Decrease of ≥ 25% from baseline in ocular staining score, or if normal score at baseline no change to abnormal Increase of ≥ 25% from baseline in stimulated salivary flow Improvement in one or more serological markers (RF, IgG, complement C3 	
	or C4, cryoglobulin)	
Additional		
To compare the efficacy of branebrutinib with PBO at Week 24 in the treatment of subjects with pSS	 Decrease of ≥ 1 point or 15% in the ESSPRI Total Score Decrease of ≥ 3 points from baseline in ESSDAI score Decrease of ≥ 25% from baseline in ocular staining score, or if normal score at baseline no change to abnormal Increase of ≥ 25% from baseline in Schirmer's test score, or if normal score at baseline no change to abnormal Increase of ≥ 25% from baseline in tear break-up time (TBUT), or if normal score at baseline no change to abnormal Increase of ≥ 25% from baseline in stimulated salivary flow Improvement in one or more serological markers (RF, IgG, complement C3 or C4, cryoglobulin) Change from baseline in autoantibody titers, hsCRP, and ESR Change from baseline in DAS28-CRP Change from baseline in the EQ-5 D-5 L score Change from baseline in PROMIS Fatigue 6 a Changes from baseline in PGA and SGA Changes from baseline in NRS for Mouth and Eye Dryness 	
• To compare the safety • To compare the safety		
and tolerability of branebrutinib with PBO in subjects with pSS	Number and proportion of subjects experiencing SAEs, AEs, and abnormalities in laboratory parameters, vital signs, and ECGs	
Exploratory I		

Protocol Amendment No.: 04 Date: 01-Dec-2021

: 01-Dec-2021

pSS Sub-protocol Overall Design:

- This is a double-blind, PBO-controlled Phase 2a study sub-protocol to evaluate the effect of branebrutinib (BMS-986195) in subjects with pSS. All subjects will receive background therapy for their primary disease as appropriate.
- Subjects will receive double-blind oral branebrutinib 9 mg or PBO treatment once daily for 24 weeks (Week 0 to Week 24).

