- Treatment assignment will be conducted by randomization. Subjects will undergo screening evaluations to determine eligibility within 28 days prior to administration of study medication. Following the screening process, if eligible for study participation, subjects will be randomized to receive branebrutinib or PBO treatment in a 2:1 ratio. Randomization will be stratified by hydroxychloroquine (HCQ) use (yes/no).

pSS Sub-protocol Number of Subjects:

It is expected that approximately 45 subjects will be randomized in the pSS sub-protocol.

Clinical Protocol
BMS-986195
IM014029 - pSS
Branebrutinib

pSS Sub-protocol Duration:

The total duration of participation in the pSS sub-protocol is approximately 32 weeks and will be divided into the following periods: screening (up to 4 weeks), double-blind PBO-controlled treatment for 24 weeks (Week 0 to Week 24), and follow-up (4 weeks).

pSS Sub-protocol Study Treatment:

Study Drug for IM014029		
Medication	Potency	IP/Non-IP
Branebrutinib	9 mg QD, oral	IP
Branebrutinib PBO	QD, oral	IP

IP = investigational product; PBO = placebo; QD = once daily

pSS Sub-protocol Statistical Methods

Sample size is calculated based on the estimated effect size for the primary endpoint comparison between branebrutinib and PBO treatment groups. The primary endpoint for the pSS sub-protocol is pSS composite response at Week 24.

Estimates for response rates were obtained from the published literature. Sample size justification is provided below:

Assuming a total sample size of 45 subjects randomized in a blinded fashion at a 2:1 ratio to branebrutinib (30 subjects) or PBO (15 subjects) and a treatment difference of 30% with a PBO response of 20% for the pSS composite response at Week 24, the 95% CI is expected to exclude 0 (expected 95% CI based on a z-test = 3%, 57%).

Categorical data will be summarized by treatment group as frequency counts and percentages. Continuous data will be summarized by treatment group using n, mean, standard deviation, median, minimum, and maximum unless otherwise specified. Efficacy data will be summarized separately for each sub-protocol and with each sub-protocol combined for variables that are similar among the sub-protocols. Primary analysis for each sub-protocol will be performed after all subjects finish the study within a sub-protocol. There will be no alpha level adjustment for multiple endpoint testing.

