The primary endpoint will be analyzed using analysis of covariance. The baseline value of the endpoint being tested will be added into the model as a covariate and HCQ use (yes/no) and treatment as fixed effects. Treatment differences based on least-squares means and corresponding 2-sided 95% CIs will be provided for the difference between branebrutinib and PBO. The mixed model repeated measures analyses may be used in supportive analyses for continuous endpoints. Bayesian borrowing to utilize historical controls may also be performed as supportive analyses. Details will be provided in the SAP if needed.

[figure not shown]
Missing data are addressed in these models and assumed to be missing at random.

TEAEs and SAEs will be summarized using counts and percentages of subjects experiencing the event as well as the number of events by system organ class, preferred term, and treatment group.

Protocol Amendment No.: 04

Physical examinations findings, vital signs, clinical laboratory test results, and electrocardiogram results will be summarized using descriptive statistics (n, mean, standard deviation, median, minimum, and maximum) for continuous variables and frequency distributions (counts and percentages) for categorical variables. Safety data will be summarized separately for each sub-protocol and with all sub-protocols combined.

pSS 1.2 Schema

ACR = American College of Rheumatology; Anti-SSA = anti-Sjögren's Syndrome-associated antigen A antibody; ESSDAI = European League Against Rheumatism Sjögren's Syndrome Disease Activity Index; ESSPRI = European League Against Rheumatism Patient-reported Index; EULAR = European League Against Rheumatism; IgG = immunoglobulin G; OSS = ocular staining score; pSS = primary Sjögren's syndrome

pSS 1.3 Schedule of Activities

pSS Table 1 Screening Procedural Outline Branebrutinib Study IM014029

Procedure	Screening (V1)	Notes		
Eligibility Assessments				
Informed Consent	X	A subject is considered enrolled only when a protocol-specific ICF is signed; this includes subjects at preselected clinical sites consenting to participate in extended PK sampling in addition to the sampling scheduled for all study subjects.		
Enroll subject in the IRT system	X			

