In vivo studies to evaluate the developmental and reproductive effects of branebrutinib have shown developmental toxicity in rabbits (at an exposure multiple of 53× relative to the dose of 9 mg proposed for this study) that were associated with maternal mortality (IB Section 4.3.5¹²). At the NOAEL of 40 mg/kg/day, the safety margin was 16× compared to the human AUC at 10 mg MAD. branebrutinib was not associated with maternal or developmental toxicity in pregnant rats at exposure multiples up to 437× (versus human AUC at 10 mg MAD). Based on the exposure safety multiple, there is minimal risk to WOCBP. However, to ensure safety, the study will require WOCBP to use highly effective contraception, and pregnant women will not be enrolled in this study. It is not known whether branebrutinib passes into human milk. Therefore, breastfeeding women will also not be enrolled in this study. The DDI study with oral contraceptives (Study IM014023) demonstrated lack of PK interaction, 47 which ensures efficacy of hormonal contraception co-administered with branebrutinib.

[figure not shown]
Clinical Protocol IM014029 - pSS BMS-986195 Branebrutinib

PSS 3 OBJECTIVES AND ENDPOINTS

pSS Table 3 Objectives and Endpoints

Objectives	Endpoints
Primary	
	Proportion of subjects with at least 3 of the following at Week 24:
	• Decrease of ≥ 1 point or 15% from baseline in the ESSPRI Total Score
To compare the efficacy of	• Decrease of ≥ 3 points from baseline in ESSDAI score
branebrutinib with PBO at Week 24 in the treatment of	• Decrease of ≥ 25% from baseline in ocular staining score, or if normal score at baseline no change to abnormal
subjects with pSS	• Increase of ≥ 25% from baseline in stimulated salivary flow
	Improvement in one or more serological markers (RF, IgG, complement C3 or C4, cryoglobulin)
Additional	
	• Decrease of ≥ 1 point or 15% in the ESSPRI Total Score
	• Decrease of ≥ 3 points from baseline in ESSDAI score
	• Decrease of ≥ 25% from baseline in ocular staining score, or if normal score at baseline no change to abnormal
	• Increase of ≥ 25% from baseline in Schirmer's test score, or if normal score at baseline no change to abnormal
	• Increase of $\geq 25\%$ from baseline in TBUT, or if normal score at baseline no change to abnormal
To compare the efficacy of branebrutinib with PBO at	• Increase of ≥ 25% from baseline in stimulated salivary flow

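### The pSS synopsis assigns ANCOVA, with the endpoint's own baseline value as covariate, to a binary Week 24 responder endpoint that has no baseline value

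*Combined protocol and SAP*

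**What the plan says.** The pSS synopsis and pSS Table 3 define the primary endpoint as "Proportion of subjects with at least 3 of the following at Week 24", followed by five criteria: ESSPRI, ESSDAI, ocular staining, stimulated salivary flow and serological markers. All are judged against baseline; one example is "Decrease of ≥ 3 points from baseline in ESSDAI score". The sample-size text in the synopsis repeats that "The primary endpoint for the pSS sub-protocol is pSS composite response at Week 24". It plans on 30 and 15 subjects, a placebo rate of 20% and a difference of 30 points, with a z-test 95% CI of 3% to 57% that is expected to leave out 0.

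The analysis paragraph that follows says: "The primary endpoint will be analyzed using analysis of covariance. The baseline value of the endpoint being tested will be added into the model". The fixed effects are treatment and HCQ use. The reported effect is a difference in least-squares means with a 95% CI. The paragraph refers to mixed models for continuous endpoints, and a separate line adds: "Missing data are addressed in these models and assumed to be missing at random". No CMH, Fisher, logistic or risk-difference method for a proportion is visible in this synopsis.

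For comparison, the SLE synopsis and Section SLE 9.4.1 give binary endpoints a CMH test stratified by the randomisation factor, Fisher's exact test when cells are too small, and nonresponder imputation. They keep ANCOVA for continuous changes from baseline.

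**The concern.** The endpoint, the sample size and the analysis do not describe the same quantity. The first two concern a proportion; the third is a model for a continuous measurement with a baseline.

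Two things follow. The named covariate does not exist for this endpoint, so someone must choose between dropping it and substituting something else, such as baseline ESSDAI or ESSPRI, and the text gives no rule for that choice. In addition, the interval from a common-variance linear model is not the interval on which the sample size was justified. In a sub-protocol of 45 subjects, that difference decides whether the planning-case interval leaves out 0.

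**Working it through.** **Inputs** (pSS synopsis): n = 30 branebrutinib and 15 placebo; placebo rate 20%; difference 30 points, so 50% on branebrutinib; randomisation stratified by HCQ use.

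**1. The plan's own figure.** Unpooled interval for two proportions:
- SE = sqrt(0.5×0.5/30 + 0.2×0.8/15) = sqrt(0.00833 + 0.01067) = 0.1378
- CI = 0.30 ± 1.96×0.1378 = 2.98% to 57.02%

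This rounds to the stated 3% to 57%. A pooled variance gives -0.4% to 60.4% and a continuity correction gives -2.0% to 62.0%, so neither matches. The sample size therefore treats the endpoint as a difference of two proportions.

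**2. The baseline covariate.** At Day 1 every change is zero. The ocular criterion has a route that zero change can satisfy ("or if normal score at baseline no change to abnormal"). The ESSDAI criterion needs an actual fall and the serological criterion an actual improvement. The ESSPRI and salivary criteria also need a real change, taking a percentage change from a starting value of zero as undefined and therefore not met. A subject then meets at most one criterion, short of three. The endpoint's baseline value is either undefined or 0 for everyone.

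**3. Consequence for the model.** Columns: intercept, treatment, HCQ use, baseline response. With the last column constant, the 4-column design matrix has rank 3. The covariate's coefficient is not estimable.

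**4. What remains after dropping it.** Least squares on the 0/1 outcome for 15/30 against 3/15, treatment only:
- residual variance = (30×0.25 + 15×0.16)/43 = 9.9/43 = 0.2302
- SE = sqrt(0.2302×(1/30 + 1/15)) = 0.152
- 95% CI on 43 degrees of freedom = -0.6% to 60.6%

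The SE ratio is 0.152/0.138 = 1.10, about 10% wider. Adding an HCQ term with a near-even split (an assumption; the documents give no split) yields 30.3 points, -0.6% to 61.2%. In a simulation of the planning case the treatment-only interval covered the true difference 96.7% of the time, so the error is towards an interval that is too wide.

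**5. Missing data, for scale only.** Assume 20% dropout in each arm, with the same response rates among completers; the documents give no dropout rate.
- Completers only, 24 against 12: 30 points, SE = sqrt(0.25/24 + 0.16/12) = 0.154, CI -0.2% to 60.2%
- Dropouts counted as nonresponders: 40% against 16% = 24 points, SE = sqrt(0.24/30 + 0.1344/15) = 0.130, CI -1.5% to 49.5%

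The rule moves the estimate by 6 points. Both intervals include 0.

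**The case against.** The strongest reply is that a synopsis is a summary. The table of contents lists Section pSS 9.4.1 Efficacy Analyses, and the copy reviewed stops in Section pSS 7.2. In the SLE sub-protocol the corresponding body section sets out the full binary method. Master Section 1.4.6.3 also leaves details of the final analyses to the SAP. A reader might infer that the pSS primary analysis is undefined; the documents do not support that, because the governing section has not been seen. Even so, the synopsis sentence is explicit, and the amendment summary says that body changes were carried into the synopsis as necessary, so the two are meant to agree.

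A reader might also infer that pSS treats dropouts as missing at random while SLE counts them as nonresponders. That contrast is weak. The SLE synopsis carries the same missing-at-random sentence beside its nonresponder rule, and in the pSS synopsis a removed figure is marked just before the sentence. Section pSS 6.7.2 already makes steroid rescue after the first 12 weeks a nonresponder outcome. That covers rescue, not dropout, but it shows responder logic in the pSS body. What stands is that no nonresponder rule for dropout or missing data is visible in the pSS synopsis.

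Finally, it would be too strong to say that nothing can be computed. Software may drop the constant column, and treatment and HCQ use then give a risk difference of essentially 30 points in the planning case. The failure is confined to the named covariate and to the variance behind the interval.

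**Conclusion.** The synopsis sentence is wrong as written. It prescribes a covariate that the endpoint does not have, and a common-variance interval that in the planning case runs from -0.6% to 60.6% where the plan's own two-proportion interval is 3% to 57%. The SE is about 10% too wide, and the planned exclusion of 0 is lost.

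These figures rest on the plan's assumed rates and arm sizes and on the baseline term simply being dropped. The absence of a nonresponder rule is a secondary point. The similarity to the SLE wording for continuous endpoints suggests text carried over, but that is an inference.

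This should be fixed. How serious it is depends on Section pSS 9.4.1: if that section gives a method for proportions, the fault is a contradiction between synopsis and body on the primary analysis; if it repeats the ANCOVA wording, the fault reaches the analysis itself.

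**What to change.** In the pSS synopsis, replace the ANCOVA sentences for the primary endpoint with wording parallel to SLE:
- a CMH test stratified by HCQ use
- the stratified difference in response rates with its 95% CI
- Fisher's exact test if expected cell counts are too small. The planning case pools to 18/45 = 40%, so about 6 placebo responders are expected under no difference, or about 3 per HCQ stratum if the strata are even (an assumption)
- nonresponder imputation for early discontinuation of study treatment, start of a prohibited therapy, or missing Week 24 data
- the existing Section pSS 6.7.2 nonresponder rule for late steroid rescue, carried over unchanged

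Limit ANCOVA (baseline, HCQ use, treatment) and the missing-at-random sentence to continuous change-from-baseline endpoints. Check Section pSS 9.4.1 and the SAP and make all three agree.

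The cost is wording only. No extra data are needed, and the sample size and the 3% to 57% planning interval stay as they are.
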